10.3 Sample Size and Power Calculations

10.3.1 Power for Primary Endpoint

The primary end-point is the rate of insulin independence 75 days after the first single donor islet infusion. Our hypothesis is that the greater engrafted mass achieved with AAT will result in a significant increase in the proportion of subjects achieving insulin independence after the first dose. In the Edmonton era, single donor insulin independence occurred in less than 10% of patients. It appears that this is increased in patients treated with T cell depletion and Etanercept to 18%. In the CIT06 study patient who received islet transplantation after kidney grafting showed an insulin independence rate of 16.7%. A similar rate of insulin independence in IAK patients is seen in the CITR registry.

Table 7 gives the statistical power to reject the null hypothesis that the insulin independence rate is $\leq 16.7\%$, assuming a sample size of 20, using one-sided binomial test with 2.5% type 1 error. Sample size calculations assume asymptotic normality. We propose that AAT treatment will achieve single donor insulin independence in 50% of patients. With 20 patients we will have approximately an 87% power to reject the null hypothesis that the insulin independence rate is $\leq 16.7\%$ using a one-sided binomial test with 2.5% type 1 error. We believe the insulin independence rate after the first single donor islet infusion is at least as high as the control (reported in the CIT-06 study) using a one-sided test. If the true insulin independence rate is 55%, we would have 94% power to reject the null hypothesis. This suggests that we have a good chance of finding meaningful trends and potentially statistically significant differences between groups using highly relevant clinical end points in this pilot trial.

Table 7 Statistical Power to Reject the Null Hypothesis

True insulin independence rate in the study	Statistical power
45%	75%
50%	87%
55%	94%
60%	98%

We have chosen to transplant 20 subjects. This will provide approximately 87% power to detect a difference of 50% insulin independence rate in islet transplanted subjects versus the estimated 16.7% insulin independence rate. Table 8 displays minimal detectable differences with 70%, 80% and 90% power. The smallest difference that can be detected with 90% power by a one-sided 2.5% level binomial test is 52% compared to 16.7%. The minimal detectable difference is 47% compared to 16.7% with 80% power. Using a one-sided test with 10% type 1 error rate, we could detect a medium effect of slightly more than 2 fold difference (38% vs. 16.7%) with 70% power.

Table 8 Minimum Detectable Difference for Insulin Independence Rate

Power	Minimum detectable difference
70%	43% vs. 16.7%
80%	47% vs. 16.7%

90%	52% vs. 16.7%
-----	---------------

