
I confirm that I have read the above protocol in the latest version. I understand it, and I will work according to the principles of current Good Clinical Practice (cGCP) as described in the United States Code of Federal Regulations (CFR) – 21 CFR Parts 45, 50, 56, and 312, and the International Conference on Harmonization (ICH) document “Guidance for Industry: E6 Good Clinical Practice: Consolidated Guidance” dated April 1996. Further, I will conduct the study in accordance with local, legal, and regulatory requirements.
 
As the site Principal Investigator, I agree to conduct protocol, “Efficacy of AAT in Islet after Kidney Transplantation,” according to good clinical practices. I agree to carry out the study by the criteria written in the protocol and understand that no changes can be made to this protocol without written permission of the sponsor.
 <hr/> 
Site Principal Investigator (Print)
 <hr/> 
Site Principal Investigator (Signature)
 
Date
	

Protocol Synopsis

Title	Multicenter Trial of the effect of AAT on Islet Transplant Engraftment and Durability after Renal Transplant
Short Title	Efficacy of AAT in Islet after Kidney Transplantation
Clinical Phase	Phase 2
IND Sponsor	[name]
IND Number	BB-IND 13804
Activation Date	Proposed 12/2016
Accrual Objective	20 transplanted (up to 28 transplant eligible)
Accrual Period	3 years
Study Duration	5 years (Accrual plus follow-up)
Study Design	Prospective, multi-center, trial assessing the benefit of alpha-1 antitrypsin (AAT) on islet transplantation in type 1 diabetic (T1D) kidney transplant recipients.
Treatment Description	Patients meeting the study entry criteria will receive 1-3 infusion(s) of in vitro cultured islets. Patients will receive three times a week AAT infusions in the peri-transplant period for three weeks. For the first islet transplant, patients will receive induction therapy with rabbit anti-thymocyte globulin (ATG, 6 mg/kg total in 5 doses) plus etanercept and will remain on their calcineurin-based maintenance immunosuppression regimen already in place for their renal allograft. Induction therapy will be basiliximab instead of ATG for 2 nd and 3 rd transplants, if applicable.

Primary Endpoints

The proportion of GLASSIA versus control subjects from CIT-06 achieving insulin independence at day 75 after the first infusion of single donor islets.

Secondary Endpoints

Insulin Utilization

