4.1 Study Endpoints

Since our primary thesis is that GLASSIA will increase islet engraftment in the early perioperative period our primary endpoint for which the study is powered is a comparison of insulin independence rates of GLASSIA treated versus control patients at day 75 post transplant. We are fortunate to have permission to utilize data from the CIT-06 trial which will allow a large number of control patients. Since our proposed trial was directly derived from CIT-06 in terms of entry criteria, treatment regimen and post transplant monitoring except for treatment with GLASSIA and related mechanistic studies, these cohorts provide us a highly relevant comparator and allow us to enroll more GLASSIA treated patients than if a randomized trial. This increases the power of the trial making it likely that we will be able to detect differences between treated and control groups should GLASSIA exert the hypothesized benefit to engraftment.

For our primary mechanistic assessment to measure engrafted functional islet mass we will rely on the frequently sampled intravenous glucose tolerance test (FSIGT) from which an AUC for insulin secretion correlates with islet mass. Each of the 24 CIT-06 patients had this test performed at day 75. Of note, we had previously considered use of a glucose potentiated arginine stimulation test for this purpose. However, no CIT-06 patients had this test performed¹³¹⁻¹³².

Because the assessment of islet graft function is dependent on complex physiologic relationships between the graft and its recipient, no single test adequately addresses the metabolic impact of the transplant. Therefore, HbA1c and the number of episodes of severe hypoglycemia will be used as clinically relevant measures of islet graft function for secondary endpoints, and additional stimulatory tests of islet graft function utilizing MMTT, glucose, and the CPGCR will be used to assess secondary endpoints. Also, the effect of islet graft function on glycemic control (HbA1c), glycemic lability (MAGE and LI), hypoglycemia (Clarke and HYPO scores), glucose variability (CGMS®), cardiovascular impact, and renal impact will be assessed as additional secondary endpoints¹³²⁻¹³⁶. Each of these were collected in CIT-06 patients and will add to the robustness of our comparison of the metabolic outcome between GLASSIA treated and control CIT-06 subjects.

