4.1.1 Primary Endpoints

Primary Clinical Endpoint

The proportion of GLASSIA versus control CIT-06 subjects achieving insulin independence at day 75 after the first infusion of single donor islets.

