10.4 Interim Analyses to Ensure Patient Safety

We will use the method for interim analyses described by Emerson and Fleming to provide cut-points for an interim analysis for futility.

We use the following notions to describe the interim analyses plan.

Let p represent the true insulin independence rate 75 days after the first single donor islet infusion. The efficacy hypothesis is

$$H_{01}: p \leq 0.167 \text{ versus } H_{a1}: p > 0.167.$$

Rejecting this null hypothesis would lead to concluding that 75 day insulin independence rate is better than 16.7% in patients who receive AAT. In order to ensure that the study provides the maximum safety information, this study will not be stopped for efficacy.

The futility hypothesis is

$$H_{02}: p \geq 0.60 \text{ versus } H_{a2}: p < 0.60.$$

Rejecting this hypothesis would lead to concluding that 75 day insulin independence rate in patients who receive AAT is not greater than 0.60. The type II error (accepting the null hypothesis when it is false) is no greater than 0.025.

Table 10 assumes two equally spaced analyses; an interim analysis is planned when 10 subjects have completed the study and a final analysis will happen when all 20 subjects have completed the study. The table provides cut-points for a recommendation for futility (reject H_{02}). Column 3 in this table (labeled “Number of insulin independence at 75 days required”) provides the largest number of observed 75 day insulin independence that would lead to recommending futility.

At the first interim analysis (when 10 subjects have completed the study) the monitoring plan would recommend for futility if no more than 2 of the first 10 transplant subjects demonstrate a insulin

independence at 75 days after their transplant.

Table 10: Sequential Monitoring Plan

Patients Accrued Fixed Sample		Number of insulin independence at 75 days required*
10	Reject H_{02}	≤ 1
20	Accept H_{01}	≤ 7

* Based on exact binomial probabilities

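### The 87% power is for a one-sample test against a fixed 16.7%; for the stated primary comparison with the 24 CIT-06 controls, power is 59% or 75% given 4/24, depending on the test.

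*Combined protocol and SAP*

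**What the plan says.** The synopsis gives the primary endpoint as "The proportion of GLASSIA versus control subjects from CIT-06 achieving insulin independence at day 75 after the first infusion of single donor islets", and Section 4.1.1 repeats it almost word for word. Section 4.1 says that "our primary endpoint for which the study is powered is a comparison of insulin independence rates of GLASSIA treated versus control patients" at day 75. On the use of CIT-06 data it adds: "This increases the power of the trial making it likely that we will be able to detect differences between treated and control groups".

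The numerical plan is one-sample. Section 10.3.1 states: "With 20 patients we will have approximately an 87% power to reject the null hypothesis that the insulin independence rate is" at most 16.7%, by a one-sided binomial test with 2.5% type I error. It describes the same figure as "approximately 87% power to detect a difference of 50% insulin independence rate in islet transplanted subjects versus the estimated 16.7% insulin independence rate", and infers from it that "we have a good chance of finding meaningful trends and potentially statistically significant differences between groups using highly relevant clinical end points". In Section 10.4 the efficacy hypothesis concerns a single rate p against 0.167: "Rejecting this null hypothesis would lead to concluding that 75 day insulin independence rate is better than 16.7% in patients who receive AAT". Table 10 accepts that null at 7 or fewer of 20, on exact binomial probabilities.

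Section 10.1.2 names two-group tests against CIT-06, but for secondary endpoints only. No two-group test and no two-group power figure is given for the primary endpoint.

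**The concern.** The endpoint asks whether GLASSIA subjects do better than the CIT-06 controls. The only decision rule asks whether their rate exceeds a constant. That constant is itself the CIT-06 estimate from 24 patients, and the rule gives it no sampling error. A reader who takes Section 4.1 together with Section 10.3.1 will naturally read 87% as the power of the controlled comparison.

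Two things are at stake. First, the same data could support a declared success under Table 10 and an inconclusive comparison with the controls. Second, because no two-group primary test is named, one could be chosen after the results are known.

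**Working it through.** **Inputs.** Treated n = 20, assumed true rate 50%, null 16.7%, one-sided 2.5% (Section 10.3.1). Controls n = 24 (Sections 1.1 and 4.1). The control count is not stated; 24 × 0.167 = 4.0, so 4/24 is assumed.

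**1. The plan's own figure.** With X ~ Bin(20, p):

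- P(X ≥ 7 | 0.167) = 0.0375 and P(X ≥ 8 | 0.167) = 0.0114. The smallest cut with size at most 2.5% is therefore 8/20, in agreement with Table 10.
- P(X ≥ 8) at p = 0.45, 0.50, 0.55, 0.60 is 0.748, 0.868, 0.942, 0.979. This is Table 7 (75/87/94/98%).
- Power of 70/80/90% is reached at p = 0.434/0.469/0.518. This is Table 8 (43/47/52%).

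The stated figures are right for a one-sample test.

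**2. Treated count needed against 4/24.** One-sided p-values:

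| Treated | Fisher | Boschloo | Barnard (pooled-z ordering) | Pooled z | Difference, Newcombe 95% CI |
|---|---|---|---|---|---|
| 8/20 | 0.082 | 0.053 | 0.051 | 0.042 | 23 points (-3 to 47) |
| 9/20 | 0.043 | 0.026 | 0.0246 | 0.020 | 28 points (1 to 51) |
| 10/20 | 0.020 | 0.012 | 0.011 | 0.009 | 33 points (6 to 56) |

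Fisher and Boschloo need 10/20. Barnard and pooled z need 9/20. No test accepts 8/20.

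**3. Power given 4/24**, as P(X ≥ cut | p), and the rate detectable at a given power:

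| | Plan (cut 8) | Cut 9 | Cut 10 |
|---|---|---|---|
| True rate 45% | 75% | 59% | 41% |
| True rate 50% | 87% | 75% | 59% |
| True rate 55% | 94% | 87% | 75% |
| True rate 60% | 98% | 94% | 87% |
| Detectable at 70% power | 43% | 48% | 53% |
| Detectable at 80% power | 47% | 52% | 57% |
| Detectable at 90% power | 52% | 57% | 62% |

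**4. Power with random controls.** Summing over X ~ Bin(20, 0.5) and Y ~ Bin(24, 1/6): Fisher 57%, Boschloo 62%, Barnard 65%. Pooled z gives 70%, but its maximum size is 3.6%, above the nominal 2.5%.

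**5. How often the rules disagree at a true 50%.** P(X = 8) = 0.120, the disagreement with Barnard or pooled z. P(X = 8 or 9) = 0.868 − 0.588 = 0.280, the disagreement with Fisher or Boschloo.

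**6. Type I error of the 8/20 rule if the true control rate is not 16.7%.** It is 1.8% at 18%, 2.5% at about 19.1%, 3.2% at 20% and 10.2% at 25%. The exact 95% interval for 4/24 is 4.7% to 37.4%.

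**The case against.** The strongest reply is that a one-sample design was intended. Section 10.3.1 says openly that the test is one-sample, Section 10.4 has the same hypothesis, Table 10 is consistent with it, and a fixed historical rate is a recognised phase 2 benchmark. That stands as a defence of the 87% itself. It does not rescue the endpoint wording in the synopsis and Sections 4.1 and 4.1.1, or the between-group inference in Section 10.3.1.

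Other points have partial force:

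- The sentence in Section 4.1 about increased power follows one saying that historical controls allow more treated patients than randomisation would. That relative claim is sound: if 20 patients were randomised 10:10, power would be about 17% (Fisher) or 31% (pooled z). The statement that the study is powered for the comparison carries no such qualification.
- CIT-06 was already complete, so the figures given 4/24 describe this trial better than the random-control figures. The 59% and 75% should lead.
- The answer depends on the test. The only between-group test for proportions in the plan is chi-square, named for secondary endpoints. Uncorrected, it needs 9/20 and gives 75%, the smallest gap.
- Every control rate the plan cites (below 10%, 16.7%, 17%, 18%) keeps the 8/20 rule within 2.5%, and the plan says the registry rate is similar. The 20% and 25% rates are sensitivity values, not evidence that the rule fails.
- The conclusion in Section 10.3.1 is hedged and the trial is called a pilot. The powering statement in Section 4.1 is not hedged.

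**Conclusion.** The concern holds. The primary endpoint and the primary test answer different questions, and 87% is the power of the test, not of the comparison that the endpoint names. At 50% versus 16.7% and one-sided 2.5%, the shortfall given 4/24 is 12 points (75%, Barnard or pooled z) or 28 points (59%, Fisher or Boschloo). No two-group method tried exceeds about 75%.

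This rests on the inferred 4/24 and on the plan's assumed 50%. It also depends on a two-group test that the plan does not specify, so results are given by method. Because the mismatch concerns the primary analysis and can change the reported conclusion, it must be settled before day-75 data are examined.

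**What to change.** Choose one.

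**(a) Make the controlled comparison primary.** Name one two-group exact test of GLASSIA versus CIT-06 (for example Barnard's or Fisher's, one-sided 2.5%) with a confidence interval for the difference. Restate Tables 7 and 8 with power both given 4/24 and with random controls. Move the final cut-point in Table 10 for accepting the null from 7 or fewer to 8 or fewer (Barnard) or 9 or fewer (Fisher, Boschloo). The cost is stated power: 75% (Barnard) or 59% (Fisher, Boschloo) in place of 87%.

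**(b) Keep the one-sample test.** Sample size, 8/20 cut and 87% all stay. Reword the synopsis and Sections 4.1 and 4.1.1 as a test against a fixed 16.7% benchmark, and remove the between-group inference from Section 10.3.1. Label the 87% as one-sample power wherever it appears. Make the CIT-06 comparison supportive, with a confidence interval for the difference, and report the rule's type I error for control rates of 18% to 25%. The cost is giving up the claim of a controlled primary comparison.

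Neither needs extra patients. Under Section 10.5, a change to a principal feature such as the primary test or cut-point needs a protocol or SAP amendment reviewed by the DSMB, the sponsor and the health authorities.

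Separately, Section 10.1.1 calls FSIGT islet mass the endpoint for which the study is powered. Correct it so that day-75 insulin independence is the single primary endpoint and FSIGT is secondary.

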10.3.2 Precision of Estimates of Secondary Endpoints

We calculate the half width of the 95% confidence interval of the mean for each secondary endpoint based on their estimated standard deviation and the sample size. That is, we can say with 95% confidence that the true value of the mean will be no further from the observed estimate than the value reported. Table 9 provides the half width of the confidence interval for HbA1c, c-Peptide, MMTT, Hypo score, MAGE and LI.

Table 9. Precision of Estimates of Secondary Endpoints

Variable	Mean	Standard Deviation	Half Width of 95% CI
HbA1c	6	0.7	0.31
c-Peptide	2	0.7	0.31
MMTT	133	55	24
Hypo Score	850	750	329
MAGE	8	4	1.8
LI	223	200	88

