A more recent analysis studied AAT treated bone marrow transplant recipients with steroid refractory GVHD, Marcondes et al utilized a modified every other day regimen of AAT (GLASSIA) that achieved stable serum AAT levels in the desired target range⁷². Their regimen consisted of a 90 mg/kg load followed by 60 mg/kg every other day for 8 doses. We have adopted a modified version of this regimen for our trial that contains a total weekly dose in the Grifols trial of 120 mg/kg/wk.

Based on the above findings, we contend that the diverse inflammation targeting properties of AAT may simultaneously impact critical impediments to islet transplantation – alloimmunity, autoimmunity, and innate/inflammation induced early post-transplant islet loss. Given that in addition to the study patients noted above, AAT has been administered safely long term to large numbers of patients as replacement therapy in the setting of AAT deficiency⁷³⁻⁷⁴, and has proven highly safe even in immunosuppressed post-lung transplant patients, in conjunction with the fact that it is readily commercially available, makes the agent an exciting therapy to improve islet transplant success.

In the current trial, we will capitalize on data from the CIT-06 trial (with permission of the CIT steering committee) that has completed enrollment of 24 IAK patients and has now passed the 1 year primary endpoint. Since the proposed cohort to be treated with AAT is otherwise similar in terms of recipient selection, islet manufacturing, medical management and post transplant follow-up, we will have a large carefully studies control cohort that will maximize trial efficiency and power to detect meaningful increases in islet mass manifest by single donor insulin independence rates at day 75. Since the day 75 single donor insulin independence rate in CIT-06 was relatively low (and nearly identical to the IAK experience in the CITR registry) at 17%, meaningful increases in engrafted mass gained by AAT therapy should be readily detectable in our study.

Use of an auxiliary islet graft in the subcutaneous tissue to monitor islet histopathology

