- HbA1c comparing GLASSIA treated versus control CIT-06 subjects at 1 year and 2 years following the *first* and *last* islet transplant(s)

Glycemic Control

- The change in Clarke score from baseline in GLASSIA treated versus control CIT-06 subjects at:
 - 1 year after the first islet transplant.
 - 2 Years after the first islet transplant
- β -score comparing GLASSIA treated versus control CIT-06 subjects at 1 year and 2 years following the *first* and *last* islet transplant(s)
- Glucose variability and hypoglycemia duration derived from the CGMS comparing GLASSIA treated versus control CIT-06 subjects at 1 year and 2 years following the first and last islet transplant(s)
- Basal (fasting) and 90-min glucose and c-peptide derived from the mixed-meal tolerance test (MMTT) comparing GLASSIA treated versus control CIT-06 subjects at 1 year and 2 years following the first and last islet transplant(s)
- MAGE comparing GLASSIA treated versus control CIT-06 subjects at 1 year and 2 years following the first and last islet transplant(s)
- Glycemic lability index (LI) comparing GLASSIA treated versus CIT-06 control subjects at 1 year and 2 years following the first and last islet transplant(s)
- Ryan hypoglycemia severity (HYPO) Score comparing GLASSIA treated versus control CIT-06 subjects at 1 year and 2 years following the first and last islet transplant(s)
- C-peptide: (glucose· creatinine) ratio (CPGCR) comparing GLASSIA treated versus control CIT-06 subjects at 1 year and 2 years following the first and last islet transplant(s)
- Rate of favorable outcome at each center preparing islets (rate of subjects with HbA1c \leq 6.5% and absence of severe hypoglycemic events from Day 28 to Day 730, or reduction in HbA1c of 1 point and absence of severe hypoglycemia from Day 28 to Day 730).

Repeat Transplants

- The proportion of subjects receiving a second islet transplant comparing GLASSIA treated versus control CIT-06 subjects at 1 year and 2 years following the first and last islet transplant(s)
- The proportion of subjects receiving a third islet transplant comparing GLASSIA treated versus control CIT-06 subjects at 1 year and 2 years following the first and last islet transplant(s)

Other Efficacy Endpoints

- Cardiovascular events [death, cerebrovascular accident (CVA), myocardial infarction (MI)] and changes in atherogenic profile for GLASSIA treated versus control subjects at 1 year and 2 years following the first and last islet transplant(s)

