9.1.3 Glycemic Lability

Glycemic lability will be assessed by both the MAGE¹³⁴ and the LI¹²⁹.

The MAGE requires 14 – 16 capillary BG measurements over two consecutive days taken before and 2 hours after breakfast, lunch, and dinner, and at bedtime with an optional measurement at 3 AM. A glycemic excursion is calculated as the absolute difference in peak and subsequent nadir (or vice versa) glucose values, with the direction (peak to nadir versus nadir to peak) determined by the first quantifiable excursion in the two day period. All excursions > 1 S.D. of the 7 – 8 glucose readings for the day in which they occurred qualify for the analysis, where they are summed and divided by the number of qualified excursions to give the MAGE in mg/dL glucose. A MAGE > 200 mg/dL is indicative of marked glycemic lability.

The LI requires 4 or more daily capillary BG measurements over a 4 week period and is calculated as the sum of all the squared differences in consecutive glucose readings divided by the hours apart the readings were determined (range 1 to 12 hours) in (mmol/L²/hr·wk⁻¹). A LI greater than or equal to the 90th percentile (433 mmol/l²/hr·wk⁻¹) of values derived from an unselected group of T1D subjects is evidence for severe glycemic lability.

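### Table 9 uses the normal instead of the t multiplier (about 7% too narrow), gives no precision for the CIT-06 comparisons, and lists MAGE without a unit on a scale that does not fit section 9.1.3

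*Combined protocol and SAP*

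**What the plan says.** Section 10.3.2 introduces Table 9 with the sentence "We calculate the half width of the 95% confidence interval of the mean for each secondary endpoint", based on an estimated SD and the sample size. It interprets the result as "we can say with 95% confidence that the true value of the mean will be no further from the observed estimate" than the tabulated value. It names no quantile, and the table prints no units. The rows give mean, SD and half-width, for example "HbA1c 6 0.7 0.31" and "c-Peptide 2 0.7 0.31". The MAGE row has mean 8, SD 4 and half-width 1.8.

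The sample size comes from section 10.3.1: "We have chosen to transplant 20 subjects". The comparator is the CIT-06 trial, which section 1.1 says has "completed enrollment of 24 IAK patients".

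Section 4.1.2 words the endpoints behind Table 9 as comparisons between cohorts, for example "HbA1c comparing GLASSIA treated versus control CIT-06 subjects at 1 year and 2 years". HYPO score, MAGE, LI, and MMTT glucose and c-peptide are worded the same way. Section 10.1.2 plans t-tests or rank tests against CIT-06. It also plans one-group estimates: an interval for the mean change from before to after transplant, and means with intervals where change is not observable or not meaningful.

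Section 9.1.3 defines MAGE in mg/dL and adds: "A MAGE > 200 mg/dL is indicative of marked glycemic lability".

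**The concern.** Table 9 is the only statement of how precisely the secondary endpoints will be estimated. Section 10.1.2 declines any multiplicity adjustment and treats favourable changes in the listed secondary endpoints as supporting evidence for a causal effect. A reader will therefore lean on the interval widths to judge what the trial can resolve. Three things limit the table for that purpose: the multiplier appears to be the normal one although the SD is estimated from 20 subjects; the table covers one group while the listed endpoints compare two; and the MAGE row is not on the scale that the protocol itself defines.

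**Working it through.** **Inputs.** SDs from Table 9; n = 20 from section 10.3.1; 24 controls from section 1.1. The documents give no CIT-06 SD and no number of controls evaluable at 1 and 2 years, so both are assumptions below.

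**Step 1: reproduce the printed figures.** Half-width = 1.960 × SD/√20 = 0.4383 × SD. For HbA1c, 0.4383 × 0.7 = 0.307, which rounds to the printed 0.31. All six rows reproduce this way.

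**Step 2: one group with t.** Half-width = t(0.975; 19) × SD/√20 = 2.093/4.472 × SD = 0.4680 × SD. The ratio to step 1 is 2.093/1.960 = 1.068. No row rounds to its printed value, so the table used the normal quantile. For 20 normal observations with the SD estimated from them, the probability that a t variable with 19 df lies within ±1.96 is 0.935, so the coverage is about 93.5%.

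**Step 3: GLASSIA minus CIT-06, 20 versus 24, equal SDs assumed.** Half-width = t(0.975; 42) × SD × √(1/20 + 1/24) = 2.018 × 0.3028 × SD = 0.6110 × SD. The ratio to the unrounded step 1 value is 0.6110/0.4383 = 1.39.

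| Row | SD | Printed | z, one group | t(19), one group | t(42), difference |
|---|---|---|---|---|---|
| HbA1c | 0.7 | 0.31 | 0.307 | 0.328 | 0.43 |
| c-Peptide | 0.7 | 0.31 | 0.307 | 0.328 | 0.43 |
| MMTT | 55 | 24 | 24.1 | 25.7 | 33.6 |
| HYPO score | 750 | 329 | 328.7 | 351 | 458 |
| MAGE (unit not printed) | 4 | 1.8 | 1.75 | 1.87 | 2.44 |
| LI | 200 | 88 | 87.7 | 93.6 | 122 |

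**Step 4: range for the difference.** Let the control SD be k times the Table 9 SD and use the Welch interval with 24 controls.

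- k = 0.5: √(1/20 + 0.25/24) = 0.2458; about 26.8 df, t = 2.053; factor 0.5045; ratio 1.15. HbA1c half-width 0.35.
- k = 1.5: √(1/20 + 2.25/24) = 0.3791; about 40.2 df, t = 2.021; factor 0.7661; ratio 1.75. HbA1c half-width 0.54.
- Equal SDs but only 20 evaluable controls: t(38) = 2.024, √(1/20 + 1/20) = 0.3162; factor 0.6402; ratio 1.46. HbA1c half-width 0.45.

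**Step 5: MAGE.** The tabulated mean of 8 is 8/200 = 4% of the threshold for marked lability in section 9.1.3. If the row was planned in mmol/L (an assumption, with a factor of 18), the mean is 8 × 18 = 144 mg/dL and the SD is 4 × 18 = 72 mg/dL. The half-width for the difference is then 0.6110 × 72 = 44 mg/dL.

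**The case against.** The strongest defence is that Table 9 does what its text says. It is presented as the interval of a mean, and section 10.1.2 plans one-group intervals. A reader might infer that 0.31 for HbA1c is a miscalculation of 0.43. The documents do not support that: these are half-widths of two different quantities, and the second is absent rather than wrong. This part of the defence stands. It is incomplete, however. For variables measured before and after transplant, the one-group interval in section 10.1.2 is for the mean change, and the variables named there cover five of the six rows (all but LI). The tabulated means look like levels (HbA1c 6, HYPO 850), and no SD of change is given.

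It can also be said that z against t is a small matter. Using z with a rounded planning SD is a common approximation, section 10.3.1 declares asymptotic normality for its own calculations, and the planned tests are t or rank tests, so no reported result inherits the 1.96. That is fair as to size. The claim of 95% confidence is still not met at n = 20, and correcting it costs nothing. For HYPO (SD/mean = 750/850 = 0.88) and LI (200/223 = 0.90), both non-negative, skewness is likely and even the t interval is approximate. Section 10.1.2 already allows transformation or rank tests.

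The 39% rests on inputs that the documents do not give. Section 4.1 confirms all 24 controls only for the day 75 FSIGT, which is not a Table 9 row. The figure therefore needs its range.

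Finally, a reader might infer that MAGE is in the wrong unit. No unit is printed, so none can be called wrong; the mmol/L reading is plausible but assumed. Nor does the missing unit affect the half-width relative to the SD.

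**Conclusion.** The point holds in three limited parts.

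- **Multiplier.** The printed half-widths use 1.96 where t(19) applies. Each is about 7% too narrow, with coverage of about 93.5% under normality. This is certain from the figures and small.
- **Missing precision.** There is none for the CIT-06 comparisons that section 4.1.2 lists. Under equal SDs and 24 evaluable controls the half-widths are about 39% wider than the unrounded one-group z values. The widening is about 15% to 75% for a control SD of 0.5 to 1.5 times the tabulated one, and about 46% with 20 evaluable controls and equal SDs. It is an omission, not an arithmetic error.
- **MAGE.** The unit is unstated, and the values are inconsistent with the mg/dL definition in section 9.1.3.

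A reader might go on to doubt the sample size. Nothing supports that: the choice of 20 subjects, the primary power in Tables 7 and 8 and the monitoring plan in Table 10 do not use Table 9. The correction should be made, but it is no obstacle to the design.

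**What to change.** Replace Table 9.

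1. Restate the one-group half-widths with t(19): HbA1c 0.33, c-peptide 0.33, MMTT 25.7, HYPO 351, MAGE 1.87 (in the table's present unit), LI 93.6. Say whether each row is a level or a change from baseline; where a change is meant, use the SD of the change.
2. Add a column for the GLASSIA minus CIT-06 difference. State the control SD and the number of evaluable controls as assumptions, or take both from the CIT-06 data, which the sponsor has permission to use.
3. Print the unit of every row, and give MAGE in mg/dL to agree with section 9.1.3. Say which quantity the MMTT row refers to, because section 4.1.2 lists fasting and 90-minute values of both glucose and c-peptide.

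The cost is one table and a sentence of text. The stated precision becomes less favourable; sample size, endpoints and tests stay as they are.
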